6.1.5.6 Assessment of Severity

The severity, or intensity, of an AE refers to the extent to which an AE affects the patient's daily activities. The intensity of the AE will be rated as mild, moderate, or severe using the following criteria:

- Mild: These events require minimal or no treatment and do not interfere with the patient's daily activities.
- Moderate: An AE that is sufficiently discomforting to interfere with normal activities.
- Severe: These events interrupt a patient's usual daily activity and may require systemic drug therapy or other treatment. Severe events are usually incapacitating.

Changes in the severity of an AE should be documented to allow an assessment of the duration of the event at each level of intensity to be performed. Adverse events characterized as intermittent do not require documentation of the onset and duration of each episode.

6.1.5.7 Assessment of Causality

The investigator's assessment of an AE's relationship to the investigational product is part of the documentation process, but it is not a factor in determining what is or is not reported in the study. If there is any doubt as to whether a clinical observation is an AE, the event should be reported.

The relationship or association of the investigational product in causing or contributing to the AE will be characterized using the following classification and criteria:

Unrelated: This relationship suggests that there is no association between the investigational product and the reported event.

Possible: This relationship suggests that treatment with the investigational product caused or contributed to the AE, i.e., the event follows a reasonable temporal sequence from the time of drug administration or follows a known response pattern to the investigational product but could also have been produced by other factors.

Probable: This relationship suggests that a reasonable temporal sequence of the event with drug administration exists and, based upon the known pharmacological action of the drug, known or previously reported adverse reactions to the drug or class of drugs, or judgment based on the investigator's clinical experience, the association of the event with the investigational product seems likely. The event disappears or decreases on cessation or reduction of the dose of investigational product.

Definite: This relationship suggests that a definite causal relationship exists between drug administration and the AE, and other conditions (concurrent illness, progression/expression of disease state, or concurrent medication reaction) do not appear to explain the event. The event reappears or worsens if the investigational product is re-administered.

6.1.5.8 Follow-up of Patients Reporting Adverse Events

All AEs must be reported in detail on the appropriate page in the eCRF and followed to satisfactory resolution, until the investigator deems the event to be chronic or not clinically significant, or until the patient is considered to be stable.

6.2 Pharmacokinetic Assessments

6.2.1 Pharmacokinetic Blood and Urine Samples

Blood for the analysis of the investigational product in plasma will be collected on Day 1 (Visit 2) and Day 21 (Visit 4 [\pm 2 days]) at the time points/intervals described in [Table 13-2](#). Collections can be performed at any time during the collection intervals. The PK blood sampling scheme may be modified on a case-by-case so as not to exceed a total blood draw limit of 8 mL/kg over 56 days, to a maximum blood draw of 50 mL. Note that the total blood drawn accounts for both blood draws for PK assessment as well as other assessments (i.e.,

clinical laboratory assessments). Urine sampling for PK assessment will be collected by using a plastic urine collection bag following the morning dosing of investigational product on Day 1 and Day 21 (Visit 4 [\pm 2 days]). Pharmacokinetic blood and urine samples may be used for future exploratory purposes outside of this study.

6.2.2 Pharmacokinetic Parameters

Population PK analysis will be performed to calculate plasma PK parameters for the investigational product. The primary plasma PK parameters for the investigational product will include the AUC, minimum plasma concentration (C_{min}), and C_{max} . Other PK parameters may be calculated, as appropriate. Details regarding population PK analysis and PK parameters will be found in the statistical analysis plan (SAP) or Population PK modeling plan.

6.3 Exploratory Efficacy Assessments

Efficacy assessments will be performed as presented in the SOE ([Appendix 13.1](#)).

6.3.1 Electroencephalogram

A 16-hour overnight video-EEG will be performed to look for changes from baseline,

([Table 13-1](#)). The 16-hour video-EEG will be conducted according to the current American Clinical Neurophysiology Society guidelines 1, 2, 4 and 5. The international 10/20 system (using all 21 electrodes) will be utilized for this study. Less than 21 electrodes may be used only in cases that there is clinical justification to do so (e.g. the presence of a scalp wound).

6.3.2 Seizure Diary

The patient's legal representative (parent[s]/caregiver[s]) will be provided with a seizure diary at the Screening Period visit (Visit 1) to record the number of seizures daily starting from the day after Visit 1 until the patient discontinues the investigational product. The seizure diaries will be assessed by the investigator as presented in the SOE ([Appendix 13.1](#)). The investigator will ensure that the seizure diary is being completed. The investigator will also review seizure counts to ensure the number of seizures is not increasing. The seizure

diaries will indicate whether spasms are still present. [REDACTED]

[REDACTED]

[REDACTED]

[REDACTED]

[REDACTED]

[REDACTED]

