The investigator will also contact the parent/caregiver by telephone on Day 12, or Day 13 or Day 14 to review seizure counts and to assess the patient's status using the above questions.

Patients will return to the study clinic on Day 7 (Visit 3 [\pm 2 days]). Starting from the PM dose on the day of Visit 3, the dose will be escalated and patients will receive the investigational product at a dose of 9 mg/kg orally twice daily. Starting on Day 15, the dose will be escalated again and patients will receive the investigational product at a dose of 15 mg/kg orally twice daily until the end of Treatment Period 1.

At Visit 2 and each visit thereafter, a record of the incidence and severity of TEAEs and SAEs will be collected and this will serve as a primary outcome criterion for this study. Other safety-related parameters such as 12-lead electrocardiogram (ECG), hematology, chemistry, physical examination, and vital signs will also be assessed at specified visits. Seizure diaries will be collected to assess spasms count prior to each visit following Visit 1.

Video-EEG will be repeated at Day 28 (Visit 5 [\pm 2 days]) (overnight video-EEG), following Treatment Period 1 for the assessment of spasms and hypsarrhythmia.

[figure not shown]
At Visit 2 and each visit thereafter, Clinical Global Impression of Change (CGI-C) will be collected from both the investigator and the parent/caregiver.

Treatment Period 2: Dose Tapering Period (Days 29 to 42):

The full dose of the investigational product will be continued until Day 28. At the start of the Dose Tapering Period on Day 29, the dose will be reduced by half. On Day 35, the dose will be reduced by half again, and on Day 42, the investigational product will be stopped. Patients will return to the study clinic on Day 42 (Visit 6 [\pm 5 days]). Refer to [Appendix 13.1](#) for list of tests/procedures.

Follow-Up Period (Day 43 to 56):

Patients will return to the study clinic on Day 56 (Visit 7 [\pm 5 days]). Refer to Appendix 13.1 for list of tests/procedures.

Figure 3-1 Study Design**3.1.1 Rationale of Study Design**

This open-label, multicenter study design allows the investigational product to be given as either add-on therapy or monotherapy. The design and choice of study population for this Phase 2 clinical study is based on the need to provide initial safety, tolerability, PK, and efficacy outcomes of the investigational product for future clinical studies.

4 Patient Selection and Withdrawal Criteria

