6.1.5.2 Serious Adverse Events

An SAE is defined as any event that results in death, is immediately life threatening, requires inpatient hospitalization or prolongation of existing hospitalization, results in persistent or significant disability/incapacity, or is a congenital anomaly/birth defect. Important medical events that may not result in death, be life threatening, or require hospitalization may be considered SAEs when, based upon appropriate medical judgment, they may jeopardize the patient or may require medical or surgical intervention to prevent one of the outcomes listed in this definition. Examples of such medical events include allergic bronchospasm requiring intensive treatment in an emergency room or at home, blood dyscrasias or doubling of seizure frequency compared to baseline over a period of 7 days or longer.

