6.1.5.3 Eliciting and Documenting Adverse Events

Adverse events will be assessed from the time the patient's legal representative (parent[s]/caregiver[s]) signs the ICF until and including the Follow-Up visit, 14 days after the last dose of the investigational product.

Serious AEs that occur more than 14 days after the last dose of the investigational product need not be reported unless the investigator considers them related to the investigational product.

At every study visit, the patient's legal representative (parent[s]/caregiver[s]) will be asked a standard nonleading question to elicit any medically-related changes in the patient's well-being. They will also be asked if the patient has been hospitalized, had any accidents, taken any new medications, or changed concomitant medication regimens (both prescription and OTC medications).

In addition to patient observations, AEs identified from any study data (e.g., laboratory values, physical examination findings, and ECG changes) or identified from review of other documents (e.g., seizure diaries) that are relevant to patient safety will be documented on the AE page in the eCRF.

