### **3.8 Evaluation of Treatment Safety**

#### **3.8.1 Adverse Events**

An AE is defined as any untoward medical occurrence in a patient enrolled into this study regardless of its causal relationship to the investigational product. The patient's legal representative (parent[s]/caregiver[s]) will be instructed to contact the investigator at any time if any symptoms develop.

A TEAE is defined as any event not present before exposure to the investigational product or any event already present that worsens in either intensity or frequency after exposure to the investigational product.

All AEs will be reported or observed during the study will be recorded on the AE form in the eCRF. The AE and SAE reporting period begins after administration of study drug through the follow up visit. The Investigator will follow-up on all AEs observed or reported by the subject up to the end of the reporting period unless the event stabilizes and follow-up is no longer necessary. The Investigator will follow-up on SAEs until they are considered resolved or the outcome is known.

The following details will be collected for AEs: description of the AE, onset date/time, action taken with study drug (dose not changed, drug interrupted, drug withdrawn, dose increased, not applicable, or unknown), date/time of resolution, any additional treatment given, outcome

(recovered/resolved, not recovered/not resolved, recovered/resolved with sequelae, recovering/resolving, fatal or unknown), severity (mild, moderate, severe), seriousness (yes, no), relationship to study drug (unrelated, possibly, probably, definitely related or unknown), and whether the AE causes early termination of the subject.

The severity of AEs will be categorized as follows:

- Mild: These events require minimal or no treatment and do not interfere with the patient's daily activities.
- Moderate: An AE that is sufficiently discomforting to interfere with normal activities.
- Severe: These events interrupt a patient's usual daily activity and may require systemic drug therapy or other treatment. Severe events are usually incapacitating.

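### No prospective seizure counts are required after the investigational product stops, although adverse events are collected to Visit 7

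*Protocol*

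**What the plan says.** **Diary.** Protocol 6.3.2 has the caregiver record seizures daily "starting from the day after Visit 1 until the patient discontinues the investigational product". SAP 6.2.2 repeats this and lists Day 42 as the last diary assessment. The schedule of events (Protocol Table 13-1, SAP Table 3-1) marks the diary at Visits 1 to 6 and at the telephone contacts, but not at Visit 7.

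**Drug stop.** Protocol 3.1 halves the dose on Day 29, then: "On Day 35, the dose will be reduced by half again, and on Day 42, the investigational product will be stopped". Follow-up covers Days 43 to 56.

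**Adverse events.** Protocol 6.1.5.3 collects them "until and including the Follow-Up visit, 14 days after the last dose of the investigational product". SAP 3.8.1 has the same end point: "The AE and SAE reporting period begins after administration of study drug through the follow up visit". The schedule marks adverse event monitoring through Visit 7.

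**Definitions that turn on frequency.** A TEAE includes a pre-existing event that becomes worse in intensity or frequency after exposure (Protocol 6.1.5.1, SAP 3.8.1). Among its examples of important medical events that may be SAEs, Protocol 6.1.5.2 gives "doubling of seizure frequency compared to baseline over a period of 7 days or longer". Protocol 6.1.5.3 names seizure diaries as one source from which adverse events are to be identified.

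**A passage that points the other way.** Protocol 3.1 states: "Seizure diaries will be collected to assess spasms count prior to each visit following Visit 1". Read literally, that includes Visit 7.

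**The concern.** The primary objective is safety, and the SAP counts TEAEs from Day 1 to Follow-Up (SAP 7.12.1). Infantile spasms are an entry requirement, so new onset cannot be the test for seizures. Deterioration from an existing level is what makes them an adverse event (Protocol 6.1.5.4), and frequency is one of the two ways to show it. The diary is the only scheduled daily count. It ends at the drug stop, while the period in which worsening would count as a TEAE or SAE continues.

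The other routes at that stage are thin:

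- No telephone contact is scheduled after Day 12, 13 or 14, so none falls between Visits 6 and 7.
- The structured questions about seizure change in Protocol 3.1 are specified for the Day 2 to 6 and Day 12 to 14 contacts.
- Visit 7 has an open adverse event question, examinations, vital signs and medication review. The schedule gives it no diary, CGI-C or EEG.

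None of these produces a 7-day count to set beside baseline. At stake is the quality of evidence on seizure worsening after the final stop: caregiver recall instead of dated daily counts.

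**Working it through.** **Inputs.** Period lengths 28, 28, 14 and 14 days, drug stop at Day 42, and Visit 7 at Day 56 ± 5 days (Protocol 3.1 and Table 13-1). A 7-day minimum for the doubling example (Protocol 6.1.5.2). 35 enrolled and at least 26 completers (Protocol 7.4).

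**1. The plan's own figure.** 28 + 28 + 14 + 14 = 84 days, which matches the stated duration. Follow-up is 56 − 42 = 14 days, which matches the 14 days after last dose in Protocol 6.1.5.3.

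**2. Days without a required diary entry.** Days 43 to 56 are 14 days; diary days required among them: 0.
- Share of Days 1 to 56: 14/56 = 25%.
- Share of the full 84 days including screening: 14/84 = 16.7%.

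**3. Seven-day windows.** A run of *d* days holds *d* − 6 windows of 7 consecutive days.
- Wholly within Days 43 to 56: 14 − 6 = 8 windows, none with diary counts.
- Straddling the stop (starting on Days 37 to 42): 6 windows, each only partly covered.
- Windows ending by Day 42, including those in the taper, are covered.

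**4. Sensitivity to the Visit 7 window and the day of last dose.** The text does not make clear whether a dose is taken on Day 42, so both readings are shown.

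| Last dose | Visit 7 | Off-drug days | Windows wholly off drug |
|---|---|---|---|
| Day 42 | Day 51 | 9 | 3 |
| Day 42 | Day 56 | 14 | 8 |
| Day 42 | Day 61 | 19 | 13 |
| Day 41 | Day 51 | 10 | 4 |
| Day 41 | Day 56 | 15 | 9 |
| Day 41 | Day 61 | 20 | 14 |

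Two non-overlapping 7-day periods fit at the nominal visit (14/7 = 2), but only one at the short end (9 days).

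**5. Early discontinuers.** If only 26 of 35 complete, 35 − 26 = 9 patients (25.7%) stop early, and their diary ends at their own discontinuation.

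**6. After the fix.** With the diary run to Visit 7, coverage of nominal follow-up goes from 0 of 14 days to 14 of 14. All 8 wholly off-drug windows and the 6 straddling windows become countable.

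**The case against.** The strongest case is that this is weaker capture, not absence. A reader might infer that worsening after withdrawal is lost. The documents do not support that: caregivers are told to contact the investigator whenever symptoms develop, an open question is asked at every visit, and Visit 7 includes a neurological examination and a medication review that could reveal new or changed seizure treatment. This stands.

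A reader might also infer that withdrawal as a whole is unobserved. It is not. The diary covers the taper, Days 29 to 42, and the SAP plans relapse tables for that period. Only the time after the final stop lacks counts. This also stands.

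The doubling of seizure frequency is an example under medical judgement, not a criterion the protocol requires to be computed from the diary. That is right, but the example is numerical and refers to baseline, so a count is the natural way to check it.

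The sentence in Protocol 3.1 sits in the description of Treatment Period 1 and may have been meant only for that period. Even if a diary is handed in at Visit 7, Protocol 6.3.2 requires no entries after the stop.

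Background seizure-drug doses may change, and ketogenic diet or vagus nerve stimulation may start, from 2 days after the stop (Protocol 5.7). Most off-drug counts could therefore be affected by other treatment. This limits attribution, not detection.

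Text after the diary descriptions is redacted, so a further rule cannot be excluded. The visible text and both schedules agree that nothing is required at Visit 7.

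**Conclusion.** The point holds as a gap in measurement and an inconsistency to reconcile. After the drug stops, seizure worsening can be reported but cannot be verified against baseline from prospective counts. The gap is nominally 14 days, 25% of the time from first dose and 16.7% of the full study, and 9 to 19 days across the Visit 7 window if the last dose is on Day 42.

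Two further inferences are not supported. The gap is not shown to be longest for early discontinuers: adverse event collection is tied to 14 days after last dose, and a case-by-case taper with continuing diary entries is possible (Protocol 4.2.2). Nor does any visible passage say that the follow-up period was designed to study rebound. The gap also applies only to time actually spent in off-drug follow-up, so it should not be assumed for all 35 patients.

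The conclusion assumes that the redacted text contains no additional diary rule. It does not threaten the validity of the study. It is a cheap improvement to the data behind the primary safety endpoint.

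**What to change.** - Reconcile Protocol 3.1, Protocol 6.3.2, the schedule of events in both documents and SAP 6.2.2, so that the existing diary continues to Visit 7, or to 14 days after last dose for early discontinuers. Mark diary review at Visit 7.
- Add a descriptive safety output of off-drug seizure counts against baseline, stating the baseline period used. Produce it in the Safety Population: the diary tables now listed in SAP section 8 use only the EAS and mEAS, and the EAS requires at least 26 days of treatment.
- Show beside the counts the date of any change in background seizure treatment, so that a reader can see whether worsening came before or after it.

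The cost is about two more weeks of caregiver entries, a diary review at a visit that already exists, wording changes in both documents, and one more table or listing. The counts will show whether seizures increased; they cannot alone show that withdrawal was the cause.

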6.3.3 Clinical Global Impression of Change

The CGI-C assessment will be performed by the investigator as presented in the SOE ([Appendix 13.1](#)). Additionally, the patient's legal representative (parent[s]/caregiver[s]) will perform the CGI-C assessment at each visit. The CGI-C is a validated instrument that allows the investigator to rate the change in a patient's condition on a 7-point scale ranging from "very much improved since the initiation of treatment" to "very much worse since the initiation of treatment." The following 7-point scale ([Spearing et al 1997](#)) will be used to evaluate the patient's condition after initiating the medication:

Table 6-1 Clinical Global Impression of Change Scale

Scale #	Impression
1	very much improved
2	much improved
3	minimally improved
4	no change
5	minimally worse
6	much worse
7	very much worse

6.4 Safety Monitoring Committee

An unblinded, independent Data Safety Monitoring Board (DSMB) will be established to provide an ongoing, independent review and assessment of safety data, to safeguard the interests and safety of the patients participating in the study.

After 5 patients have completed Treatment Period 1, patient screening and enrollment will be halted and available safety data will be reviewed and assessed by the DSMB. Patient screening and enrollment can continue again following the DSMB's review and assessment of the safety data.

The frequency of DSMB data review meetings will be based on patient accruals. The first DSMB data review meeting will be held after 5 patients have completed Treatment Period 1. The second DSMB data review meeting will be held after 5 additional patients have completed Treatment Period 1 (after a total of 10 patients have completed Treatment Period 1). The third DSMB data review meeting will be held after 10 additional patients have completed Treatment Period 1 (after a total of 20 patients have completed Treatment Period 1), and the fourth DSMB data review meeting will be held after 10 additional patients have completed Treatment Period 1 (after a total of 30 patients have completed Treatment Period 1).

The committee may request additional meetings if it is deemed appropriate based on trends identified within the current data. The sponsor's designee will be responsible for scheduling this type of meeting.

The DSMB will adhere to a prospectively determined charter, which will be written by the sponsor and approved by the DSMB. The charter will define the responsibilities of the DSMB and sponsor, describe the conduct and frequency of the meetings and define the data sets to be reviewed. In addition, a special DSMB meeting will be convened if the safety-related study stopping rules are met and all serious TEAEs, TEAEs leading to investigational product discontinuation, and TEAEs leading to death will be reviewed.

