4.1 Selection of Study Population

Approximately 50 patients will be screened of which, approximately 35 patients will be enrolled to target at least 26 patients as study completers at the appropriate number of study sites in the United States and Republic of Korea. At least 7 of the patients enrolled must be between 6 months through 12 months of age at the time of informed consent. Patients will be assigned to study treatment only if they meet all of the inclusion criteria and none of the exclusion criteria.

Deviations from the inclusion and exclusion criteria are not allowed because they can potentially jeopardize the scientific integrity of the study, regulatory acceptability, or patient safety. Therefore, adherence to the criteria as specified in the protocol is essential.

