4.2.3 Replacements

A total of approximately 50 patients will be screened of which around 35 patients will be enrolled to provide at least 26 completers. At least 7 of the patients enrolled must be between 6 months through 12 months of age at the time of informed consent. Patient screening and enrollment will be closed after 35 patients have begun Treatment Period 1. Patients who discontinue the study for any reason after dosing will not be replaced.

5 Study Treatments

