7.4 Sample Size Calculations

Approximately 50 patients will be screened of which around 35 patients will be enrolled to provide at least 26 completers. At least 7 of the patients enrolled must be between 6 months through 12 months of age at the time of informed consent. Patients who are screened and not dosed will be replaced. Patients who discontinue the study for any reason after dosing will not be replaced.

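### Scheduled DSMB reviews and the enrolment pause count only patients who complete Treatment Period 1, so early discontinuations delay them and the fourth review is not assured

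*Protocol*

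**What the plan says.** Protocol section 6.4 lists four scheduled DSMB data reviews. The first reads: "The first DSMB data review meeting will be held after 5 patients have completed Treatment Period 1". The second and third follow at cumulative totals of 10 and 20, and the fourth comes "after a total of 30 patients have completed Treatment Period 1". The one enrolment pause is tied to the first count: "After 5 patients have completed Treatment Period 1, patient screening and enrollment will be halted". The same section says that meeting frequency follows patient accrual, although every listed trigger counts completions.

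Section 6.4 also gives two routes to a meeting that need no completer count. One is discretionary: "The committee may request additional meetings if it is deemed appropriate based on trends identified within the current data". The other is a special meeting if the study's safety stopping rules are met. The section adds that serious, treatment-stopping and fatal TEAEs will be reviewed. Section 11.1.1 refers frequency to the DSMB charter.

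On numbers, section 7.4 says that "around 35 patients will be enrolled to provide at least 26 completers". Section 4.1 makes clear that these are study completers: "to target at least 26 patients as study completers". Section 4.2.3 fixes the ceiling, "Patient screening and enrollment will be closed after 35 patients have begun Treatment Period 1", and rules out replacement: "Patients who discontinue the study for any reason after dosing will not be replaced".

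**The concern.** Safety and tolerability are the primary objective, and both dose escalations fall inside Treatment Period 1. A child who does not tolerate an escalation and stops is the kind of case the DSMB should see early. Yet that child brings neither the first review nor the pause closer; another patient has to start and finish 28 days instead. The trigger therefore slows as tolerability worsens, and section 6.4 sets no limit on how many patients may be dosed before the pause.

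The last trigger raises a separate problem. Thirty completers is four more than the minimum the plan sets itself, from a fixed pool of 35. If 30 is not reached, no scheduled review follows the one at 20 completers.

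**Working it through.** **Inputs.** Triggers of 5, 10, 20 and 30 Treatment Period 1 completers (protocol 6.4). Enrolment closed after 35 starters, with no replacement after dosing (4.2.3). Target of at least 26 study completers (4.1, 7.4). The visible text gives no dropout rate, and part of SAP 7.13 is redacted. Completion rates other than 26/35 and 30/35 are therefore assumptions, shown as a range.

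**The plan's own figure.** 26/35 = 74.3%, an allowance of 9/35 = 25.7% for loss. Inflating 26 for 25% loss gives 26/0.75 = 34.7, rounded up to 35, so the two figures fit together. The 25.7% is itself back-calculated from them, so this is a consistency check and not an independent reproduction.

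**Delay to the first review and the pause.** Let p be the chance that a starter completes Treatment Period 1, independently between patients. The number of starters needed for 5 completers is negative binomial with mean 5/p.

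| p | Mean starters | 95th percentile |
|---|---|---|
| 30/35 | 5.8 | 8 |
| 26/35 | 6.7 | 10 |
| 0.50 (assumed) | 10 | 16 |

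Patients still within their 28 days when the fifth completer finishes are additional.

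**Chance of reaching the fourth review.** Thirty of 35 is 85.7%. With X ~ Binomial(35, p):

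| p | P(X ≥ 30) |
|---|---|
| 26/35 | 8.2% |
| 0.80 | 27.2% |
| 0.85 | 56.9% |
| 30/35 | 61.6% |
| 0.90 | 86.8% |

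The third review is not in doubt: P(X ≥ 20) = 99.2% at p = 26/35.

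**Sensitivity to what 26 means.** The 8.2% takes 26 as the expected number and puts every loss inside Treatment Period 1. Two other readings fit the text.

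- *26 as a floor to be met with high probability, all losses in Treatment Period 1.* Solving P(X ≥ 26) = 80%, 90% or 95% gives p = 0.786, 0.814 or 0.836. P(X ≥ 30) is then 21%, 35% or 48%.
- *Nine losses expected, k of them after Treatment Period 1.* Here p = (26 + k)/35, and P(X ≥ 30) is 27.2% for k = 2, 61.6% for k = 4 and 92.5% for k = 6.

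**Effect of the remedy.** If discontinuations during Treatment Period 1 also count, the first trigger is met when the fifth starter's Treatment Period 1 outcome is known. That is 6.7 − 5 = 1.7 fewer starters on average at 26/35, and 10 − 5 = 5 fewer at 50%. With 35 starters, each of whom must either complete or discontinue, the count of 30 is always reached.

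**The case against.** The strongest reply is that scheduled counts are not the DSMB's only way in. The committee can ask for a meeting, and a stopping-rule meeting is mandatory once the rules are met. The events to be reviewed expressly include TEAEs that lead to discontinuation, and the DSMB reviews the available safety data, not only completers' data. A reader might infer that no review can happen without the completer count; section 6.4 does not support that. The point that remains is narrower. The requested meeting is discretionary, the stopping rules do not appear in the supplied text (the charter, which is not supplied, may hold them), and neither route is stated to pause enrolment.

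A reader might also infer that the plan's own figures make the fourth review unlikely. They do not. Twenty-six is a minimum, and it counts patients who complete the study, which runs through taper and follow-up to Day 56. Treatment Period 1 completers can only equal or exceed that number. The 8% needs two assumptions that the plan does not make.

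On size, the delay at 26/35 is under two patients on average, and nothing in the documents predicts 50% completion. The fourth review would come when at least 30 of 35 patients have been dosed, so it can affect few enrolment decisions. Both observations stand and limit the weight of the point.

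Finally, counting completers has a merit: the one mandated pause is certain to rest on five patients followed through the second escalation on Day 15 and on to the end of the period. That is a real trade-off, and it should be stated with the change.

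**Conclusion.** The point holds for the scheduled reviews and the enrolment pause. Discontinuation during Treatment Period 1 delays both, at any completion rate below 100%. The delay is small at the planned rate (mean 6.7 starters for 5 completers, 95th percentile 10) and larger if tolerability is poor (mean 10, 95th percentile 16, at an assumed 50%), before adding patients still in treatment.

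The fourth review is not assured. Depending on the completion rate and on when losses occur, its probability runs from 8% to above 90%. The low end applies only if 26/35 is the Treatment Period 1 completion rate. All figures assume 35 starters and independent outcomes. This is a cheap improvement to the timing of oversight; the documents do not show that safety review is absent.

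**What to change.** In protocol section 6.4 and the DSMB charter, trigger each scheduled review, and the pause, when 5, 10, 20 and 30 treated patients have either completed Treatment Period 1 or discontinued during it. Reconcile the statement that frequency follows accrual with whichever count is kept.

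The cost is about one sentence in each document, with no extra patients or procedures. Reviews would fall at the same time or earlier. The downside is that the first review, and the pause with it, may include fewer than five patients followed through all of Treatment Period 1. Each DSMB report should therefore state how many were followed throughout and how many stopped early.

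The change does not cap the number of patients in treatment before the first review. If the sponsor wants a cap, it needs a separate provision.
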